### 3.1 EVALUATION OF CLINICAL CHARACTERISTICS

Evaluation and comparison of the main study parameters for the following groups:

- Males vs. females
- Young (<65 years) vs. old ( $\geq 65$  years)
- Age at risk:  $\geq 55$  years in males and age  $\geq 65$  years in females
- Ethnicity
- Smoking (smoker, no smoker, ex-smoker)
- Alcohol (yes vs. no)
- Coffee or tea (yes vs. no)
- Smoking or alcohol or coffee (yes vs. no)
- Family history for cardiovascular disease (yes vs. no)
- Previous cardiovascular diseases (yes vs. no)
- Any previous medical condition (yes vs. no)
- Arterial hypertension (untreated and treated)
- Antihypertensive treatment (yes vs. no)
- Dyslipidemia (untreated and treated)
- Lipid lowering treatment (yes vs. no)
- Diabetes (untreated and treated)
- Treatment of diabetes (yes vs. no)
- Metabolic syndrome (yes vs. no)
- Any cardiovascular disease (TIA, stroke, myocardial infarction, etc.) (yes vs. no)

Race will be modified according to the following rule in order to calculate ethnicity (missing values will be recoded into an appropriate value and if no category can be identified the “Caucasian” group will be assigned)

- Caucasian (1)
- Black (2)
- Asian (3)
- Hispanic (4)

In case of missing value for the following variables the missing value will be recoded to 0:

- Smoking
- Alcohol
- Coffee
- Left ventricular Hypertrophy at the ECG
- Family history for any CV disease
- Hypertension and therapy
- Number of antihypertensive drugs
- Dyslipidemia and therapy

- Diabetes and therapy
- Concomitant diseases and treatments
- Cardiovascular disease
- Cardiovascular risk
- Component of the metabolic syndrome and metabolic syndrome

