### 3.2 EVALUATION OF THE METABOLIC SYNDROME

The metabolic syndrome will be evaluated according to the harmonized definition [Alberti KG, Eckel RH, Grundy SM, Zimmet PZ, Cleeman JI, Donato KA, Fruchart JC, James WP, Loria CM, Smith SC Jr; International Diabetes Federation Task Force on Epidemiology and Prevention; National Heart, Lung, and Blood Institute; American Heart Association; World Heart Federation; International Atherosclerosis Society; International Association for the Study of Obesity. Harmonizing the metabolic syndrome: a joint interim statement of the International Diabetes Federation Task Force on Epidemiology and Prevention; National Heart, Lung, and Blood Institute; American Heart Association; World Heart Federation; International Atherosclerosis Society; and International Association for the Study of Obesity. Circulation. 2009 Oct 20;120(16):1640-5]. Presence of 3 out of 5 of the following risk factors

a) Elevated waist circumference (Caucasian)

≥94 cm in males  
≥80 cm in females

Elevated waist circumference (South America and Asia)

≥90 cm in males  
≥80 cm in females

When waist circumference is missing a BMI  $\geq 25 \text{ kg/m}^2$  will be used

- b) Elevated triglycerides ( $\geq 150 \text{ mg/dL}$ ) or lipid-lowering treatment
- c) Reduced HDL cholesterol ( $< 40 \text{ mg/dL}$  males and  $< 50 \text{ mg/dL}$  females) or lipid-lowering treatment
- d) Elevated blood pressure ( $\geq 130 / 80 \text{ mmHg}$ ) or antihypertensive treatment
- e) Elevated fasting glucose ( $\geq 100 \text{ mg/dL}$ ) or treatment for diabetes

In case of missing HDL it will be calculated in presence of total cholesterol, LDL cholesterol and triglycerides as

$$\text{HDL} = \text{Total cholesterol} - \text{LDL cholesterol} - \text{Triglycerides} / 5$$

Also Cholesterol LDL and Triglycerides, if missing, will be recalculated starting from the available parameters.

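### Patients whose ethnicity cannot be identified are analysed as Caucasian, and the ethnicity codes are not mapped to the waist cut-offs

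*SAP*

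**What the plan says.** SAP 3.1 derives ethnicity from race in four codes: Caucasian (1), Black (2), Asian (3) and Hispanic (4). For gaps it states that "missing values will be recoded into an appropriate value and if no category can be identified the" Caucasian group is assigned. The section is introduced as "Evaluation and comparison of the main study parameters for the following groups", and ethnicity is one of the groups listed. It gives no unknown level, no limit on how often the default may be used, and no sensitivity analysis.

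SAP 3.1 also lists variables whose missing values are set to 0. The last item is "Component of the metabolic syndrome and metabolic syndrome".

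The SAP section on the metabolic syndrome (the second section numbered 3.2) requires three of five components. The waist component has two sets of cut-offs. One is headed "Elevated waist circumference (Caucasian" and uses "≥94 cm in males"; the other is headed "Elevated waist circumference (South America and Asia" and uses "≥90 cm in males". Women have 80 cm in both sets. If waist was not measured, a BMI of at least 25 is used for everyone. The section does not say which ethnicity codes use which set, and it has no set for code 2.

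**The concern.** The default replaces an unknown with one particular answer and then treats that answer as data. Non-Caucasian patients without an identifiable category move into the Caucasian group. That group's mean is pulled toward the others, the smaller groups lose patients, and the standard errors are computed as if every classification had been observed.

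Gaps are plausible. The registry draws on existing databases (Protocol 9.0) and foresees no formal monitoring (Protocol 14.2), and the rule itself anticipates missing values. It may also catch patients who fit none of the four codes, and their ethnicity would not be missing at random.

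The same variable may feed the metabolic-syndrome definition, which belongs to the main analysis in SAP 3. The male cut-offs differ by 4 cm, so a recoded man can be scored against the higher one.

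**Working it through.** The documents give no missing rate, ethnic mix or waist distribution, so there is no stated figure to reproduce. The calculation uses ranges.

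**Inputs**
- Registry size: at least 30 centers with at least 100 patients each (Protocol 4.0), so 30 × 100 = 3,000.
- m, share with ethnicity still unidentified: 5-20% (assumed).
- p, true non-Caucasian share: 5-20% (assumed).
- Missingness unrelated to ethnicity (assumed).
- Half of patients are men (assumed).
- Male waist normal with mean 92-100 cm and SD 10-12 cm (assumed).
- Male cut-offs 94 and 90 cm, female cut-off 80 cm in both sets (SAP, metabolic syndrome).

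**Step 1: the ethnicity comparison.** The misassigned share of the Caucasian group is c = m·p / [(1−p)(1−m) + m].

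| m | p | c |
|---|---|---|
| 5% | 5% | 0.0025 / 0.9525 = 0.26% |
| 20% | 5% | 0.0100 / 0.9600 = 1.0% |
| 5% | 20% | 0.0100 / 0.8100 = 1.2% |
| 20% | 20% | 0.0400 / 0.8400 = 4.8% |

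A Caucasian versus non-Caucasian mean difference shrinks by the factor 1−c, from 0.997 down to 0.952. The non-Caucasian groups together lose the share m of their members: 3,000 × m × p = 7.5 to 120 patients. On a wider grid (m 1-20%, p 2-30%), c runs from 0.02% to 7.9%.

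**Step 2: who can change on the waist component.**
- Women cannot, because both sets use 80 cm.
- Patients classified by BMI cannot, because that rule ignores ethnicity.
- Unknowns who are truly Caucasian (80-95% of unknowns under these assumptions) receive the set written for them.
- Truly Asian or South American/Hispanic men recoded as Caucasian, with a waist of 90 to under 94 cm, change from elevated to not elevated. The error runs in this direction only.

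This requires that the recoded ethnicity variable selects the set, which the SAP does not state.

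**Step 3: how many.** P(90 ≤ waist < 94) is 10.6% at mean 100, SD 12, and 15.9% at mean 92, SD 10, so about 11-16%. Counting every non-Caucasian patient as Asian or Hispanic, which gives an upper limit, the expected number is 3,000 × m × p × 0.5 × band:
- low: 3,000 × 0.05 × 0.05 × 0.5 × 0.11 = 0.4
- high: 3,000 × 0.20 × 0.20 × 0.5 × 0.16 = 9.6

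**Step 4: syndrome status.** A changed waist component alters the diagnosis only when exactly two of the other four are present. If that holds for 30-40% (assumed), the high case gives 9.6 × 0.3 to 9.6 × 0.4, about 3 to 4 patients.

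**Step 5: the Black code.** Code 2 exists in SAP 3.1 but has no waist set. A patient in this group without a waist measurement is classified by BMI; one with a measurement has no rule. If the programmer treats the undefined result as missing, the recode list turns it into 0. If the programmer applies either existing set, it is scored normally. The SAP does not decide between these.

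**The case against.** The default is a last resort: a missing value is first to be given an appropriate category. Ethnicity is among the required inclusion data (Protocol 4.0 and 9.1 with 14.1), the CRF must be completed for it (SAP 2.2), and missing entries are checked and raised with investigators (Protocol 14.1 and 14.2). Recruitment starts in Italy and Russia (Protocol 12.3). Ethnicity is one of 19 groupings in SAP 3.1, with no hypothesis attached. All of this stands as a reason to expect a small effect, and the 5-20% missing rate may well be too high. It does not justify the rule, which still analyses an unknown as an observation.

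On the syndrome, a hypertensive patient on lipid-lowering treatment already meets three components (blood pressure, triglycerides, HDL) whatever the waist. That also stands, and it is a further reason why few diagnoses would change.

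A reader might infer three stronger points that the documents do not support:
- *The wrong waist cut-off is applied to unknowns in general.* Step 2 rules this out for women, for BMI-classified patients and for unknowns who are truly Caucasian.
- *Some 11-16% of men would flip.* That band applies only to men who are both unidentified and truly Asian or South American/Hispanic.
- *Black patients could never meet the waist component.* The BMI fallback applies when waist is missing, and the SAP does not say that an undefined cut-off counts as a missing value.

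**Conclusion.** The concern holds in a limited form. The Caucasian default is a wrong rule rather than a missing detail: followed as written, it dilutes the Caucasian versus non-Caucasian contrast and claims certainty that the data do not have. The likely size is small, 0.3-4.8% of the Caucasian group under the assumed 5-20% ranges, with missingness unrelated to ethnicity. It would grow as the registry extends to more diverse countries.

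The waist consequence is conditional on the recoded variable selecting the cut-off set. It is confined to a narrow group of men and reaches at most about 10 of 3,000 patients under the same assumptions.

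The absence of a mapping from codes to waist sets, including the absence of any set for the Black code, is a separate specification gap. It concerns patients whose ethnicity is known and does not follow from the Caucasian default. As written, the outcome for measured waists in that group is left to programming and could become 0.

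**What to change.** 1. In SAP 3.1, replace the Caucasian default with an unknown category. Report its frequency and leave it out of the ethnicity comparison. Misassignment by the default is then zero by construction.
2. For the waist component, classify men of unknown ethnicity under both existing cut-off sets as a sensitivity analysis, and state in advance which classification the main tables use. Women need no such analysis.
3. In the metabolic-syndrome section, map every ethnicity code, including the Black code and the unknown category, to a waist rule, so that the recode-to-0 list does not settle it by accident. Which rule to use is for the SAP's authors to decide.

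The cost is SAP wording and a changed derivation, with no new data. Patients of unknown ethnicity leave the ethnicity comparison: 3,000 × 5% = 150 to 3,000 × 20% = 600 at the assumed rates, fewer if missingness is lower. This change does not remove them from any other analysis.

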### 3. ANALYSIS

The main analysis will assess:

- The general clinical characteristics of the population
- The relationship between BP and arterial stiffness and target organ damage / cardiovascular events
- The features of BP and arterial stiffness in presence of the metabolic syndrome

The following inclusion criteria will be considered:

- Male and female aged  $\geq 18$  years
- Good quality ABPM: i) at least 70% of the number of the expected readings over the 24 hours (discarded), ii) at least 20 valid measurements during the daytime and 7 during the nighttime

The parameters assessed will be:

- 24-hour average brachial SBP and DBP
- 24-hour average aortic SBP and DBP
- 24-hour average PWV
- 24-hour average aortic AI

- 24-hour wSD of SBP and DBP
- 24-hour ARV of SBP and DBP

Analysis will be done also for the day-time and night-time subperiods.

In each individual PWV will be normalized to a SBP of 100 mmHg and a HR of 60 bpm by a regression analysis of 24-hour PWV to 24-hour SBP and 24-hour HR. AI will be normalized to a HR of 75 bpm with the same procedure.

Statistical tests to be used will include analysis of variance (ANOVA) or covariance (ANCOVA) for continuous variables with adjustments for confounding factors. Discrete variables will be analyzed by Chi-square test or logistic regression analysis. Survival analysis will be carried out by Kaplan-Meier plots, log rank test and Cox regression.

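### SAP 3.1 recodes missing values to an undefined 0; if 0 means 'no', patients without laboratory values are counted as free of the metabolic syndrome

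*SAP*

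**What the plan says.** SAP section 3.1 lists 19 groupings in which the main blood pressure and stiffness parameters will be compared. It then gives the rule "In case of missing value for the following variables the missing value will be recoded to 0". The list that follows has 13 entries: smoking, alcohol, coffee, ECG left ventricular hypertrophy, family history, hypertension and therapy, number of antihypertensive drugs, dyslipidemia and therapy, diabetes and therapy, concomitant diseases and treatments, cardiovascular disease, cardiovascular risk, and "Component of the metabolic syndrome and metabolic syndrome". None of these has a code list. Only ethnicity has codes (1 to 4), with its own default. Neither document plans a missing category, an available-case analysis, imputation or a sensitivity analysis for these variables.

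SAP section 3 names three main analyses. One is "The features of BP and arterial stiffness in presence of the metabolic syndrome". The SAP section on the metabolic syndrome requires "Presence of 3 out of 5 of the following risk factors". It substitutes BMI for a missing waist and recalculates some missing lipids from other lipids.

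Several provisions should limit blanks:
- Protocol 9.1 makes availability of the clinical data listed in Protocol 14.1 an inclusion criterion.
- SAP 2.2 makes completion of its CRF list compulsory.
- Protocol 14.1 and 14.2 provide for checks and queries on missing data, though no formal monitoring.

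**The concern.** A blank means that the state is not known. Setting it to 0 turns it into a value, and for a yes/no item the natural reading of that value is 'no'. The reported prevalence then cannot rise, and it falls as soon as one affected patient has a blank. The unaffected group also takes in affected patients, so its mean outcome moves.

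For three-level smoking, for hypertension, dyslipidemia and diabetes (each split into untreated and treated), and for cardiovascular risk, 0 has no evident meaning. Two programmers could code it differently.

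The rule acts directly on two of the three main analyses: the comparisons of clinical characteristics and the metabolic syndrome. The syndrome is the more exposed because it is a count with a threshold. A missing component set to 0 can only lower the count, and the syndrome variable is itself on the list.

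**Working it through.** The plan states no missingness rate and no figure to reproduce. The steps below rest on the SAP's own rules and, where marked, on assumptions.

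**1. Reach.** Of the 19 groupings, four are not recoded to 0: sex, the two age groupings and ethnicity. That leaves 19 − 4 = 15. Matching strictly by name gives 14, because 'any previous medical condition' reaches the list only through concomitant diseases. The 15 divide as follows:
- Five yes/no groupings where 0 = 'no' is natural: alcohol, coffee or tea, the smoking/alcohol/coffee composite, family history, metabolic syndrome.
- Four where 0 is undefined: smoking, hypertension, dyslipidemia, diabetes.
- Six that may come from disease or drug lists, where a blank may truly mean 'none': previous cardiovascular disease, any previous condition, any cardiovascular disease, and the three treatment groupings.

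**2. Metabolic syndrome, from the SAP's rules alone.** Triglycerides, HDL and glucose are not itemised in the CRF lists of Protocol 14.1 or SAP 2.2, although Protocol 10.1 mentions laboratory tests in general. Take a patient with none of the three and no lipid or diabetes treatment. Only waist (or BMI) and blood pressure can be positive, so the score is at most 2 of 5 and the patient is always 'no'. The SAP's lipid formula does not help. Without HDL and triglycerides it is one equation in two unknowns, and glucose has no substitute.

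**3. Metabolic syndrome, illustrative size.** Assumed, in BP-positive patients: raised waist 0.6, each laboratory component 0.3, independence, no diabetes treatment, and a fraction m of patients not on lipid treatment lacking all laboratory values.
- P(at least 2 of the other 4) = 0.216 + 0.6 × 0.441 = 0.481.
- A lipid-treated patient has both lipid components plus blood pressure, so is 'yes'. With a share t treated, true = t + (1 − t) × 0.481 and reported = t + (1 − t) × 0.481 × (1 − m).

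| t | True | Reported, m = 0.05 | Reported, m = 0.30 |
|---|---|---|---|
| 0 | 48% | 46% | 34% |
| 0.2 | 58% | 57% | 47% |
| 0.4 | 69% | 67% | 60% |

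False negatives within the 'no' group = 0.481m / (0.481m + 0.519), which is 4% at m = 0.05 and 22% at m = 0.30. With waist 0.5-0.7 and laboratory components 0.2-0.4, the range is 2-36%.

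**4. Other yes/no items, missing completely at random.** Reported prevalence = p(1 − m). At p = 0.20 this is 0.19 at m = 0.05 and 0.14 at m = 0.30. The mean difference shrinks by mp / [(1 − p) + mp]:

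| p | m = 0.05 | m = 0.10 | m = 0.20 | m = 0.30 |
|---|---|---|---|---|
| 0.2 | 1.2% | 2.4% | 4.8% | 7.0% |
| 0.4 | 3.2% | 6.3% | 11.8% | 16.7% |

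**5. Missingness tied to the outcome.** Assumed: true difference 0.30 SD, p = 0.2 or 0.4, log-odds of missing changing by −0.5 to +0.5 per SD of outcome. By numerical integration the 0-recode gives 0.20-0.35 SD at m = 0.05-0.10 and 0.04-0.44 SD over m = 0.05-0.30. Available-case analysis gives 0.29-0.30 SD throughout.

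**6. Only truly unaffected patients blank.** The 0-recode is then correct. Available-case prevalence would be p/(1 − m), so a true 20% becomes 21% (0.20/0.95) to 29% (0.20/0.70).

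**The case against.** The strongest reply concerns reach. A reader might infer from '15 of 19' that most of section 3.1 is biased. The documents do not support that. Six of the groupings may be list-type, where 0 can be right, and four turn on an undefined code, possibly held in a data dictionary that is not shown. Of the five natural yes/no groupings, four rest on items that are compulsory in the CRF, required for inclusion and open to query. In a patient entered according to protocol they should seldom be blank. This stands.

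A reader might also infer that the SAP drops the data-availability criterion. SAP section 2 calls its account brief and refers to the protocol for detail, so that does not follow. Where section 3 says "The following inclusion criteria will be considered", it names only age and ABPM quality, so the SAP has no second screen for blanks. Whatever survives entry and queries still goes to 0.

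A third inference is that the organ-damage and event analyses are compromised. LVMI, IMT, ankle-brachial index, eGFR, albuminuria and follow-up events are not in the rule. It reaches those analyses only through recoded covariates or "Left ventricular Hypertrophy at the ECG", which SAP 3.2.1 treats as an additional attempt.

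Finally, the 0.04-0.44 SD range should not be read as an expected effect. It is unadjusted and assumes that missingness depends directly on the outcome, for which the documents give no evidence. The SAP plans adjustment for confounders. If missingness instead ran through a covariate that is adjusted for, only the random-missingness shrinkage would remain: 0.25-0.29 SD for a true 0.30, at 10-30% missing and prevalence 20-40%.

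None of this rescues the metabolic syndrome result in step 2, which needs no assumed rate to show the misclassification.

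**Conclusion.** The concern holds, with its weight on the metabolic syndrome, and should be fixed. The rule is explicit, and under the 0 = 'no' reading it forces 'no' on a definable set of patients in a main analysis. How many there are is unknown. The 48% reported as 46% to 34% rests on the assumed component frequencies, on 5% to 30% without laboratory values, and on nobody being lipid-treated; with 20% or 40% treated the loss is smaller. For the remaining yes/no items the likely effect is modest if few values are missing, with 1-6% shrinkage at 5-10% missing completely at random and prevalence 20-40%. It is larger, and of unknown direction, if missingness depends on the outcome. Where blanks are truly unaffected there is no error. The undefined codes are a separate, plain gap that needs closing whatever the missingness rate.

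**What to change.** Delete the recode-to-0 rule and replace it as follows.

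- Keep missing as missing, and report missing counts by variable and centre.
- Allow 0 only for list-type items whose form section is documented as completed.
- State what each code means, including smoking, the untreated/treated variables and cardiovascular risk.
- Code the metabolic syndrome 'yes' with at least 3 known positive components, 'no' with at least 3 known negative, and missing otherwise.
- Do not make the available-case prevalence of the syndrome the main figure. Lipid-treated, BP-positive patients are always classifiable, while untreated patients without laboratory values drop out. With the inputs of step 3 and m = 0.30, the result is [t + (1 − t) × 0.481 × 0.7] / [t + (1 − t) × 0.7]. At t = 0.2 this is 0.469/0.76 = 62% against a true 58%; at t = 0.4 it is 0.602/0.82 = 73% against a true 69%. Instead, impute the components conditional on treatment, waist or BMI, blood pressure, the stiffness measures and centre, or report prevalence by lipid-treatment status and reweight.
- For the other section 3.1 comparisons use available-case analysis or multiple imputation, with the 0-recode as a sensitivity analysis.

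The cost is SAP wording, programming and an imputation model; no new data are needed. Intervals widen somewhat. In simulations with 3,000 patients, one binary variable and a correctly specified imputation model, which is a favourable case, standard errors were 3-24% larger than with full data. The missing-at-random assumption cannot be tested and should be stated.

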### 3.2 EVALUATION OF TARGET ORGAN DAMAGE

#### 3.2.1 CARDIAC DAMAGE

Cardiac damage will be based on LVMI, calculated as LVM divided by BSA, as follows [Devereux RB, Alonso DR, Lutas EM, Gottlieb GJ, Campo E, Sachs I, Reichel N. Echocardiographic assessment of left ventricular hypertrophy: comparison to necropsy findings. Am J Cardiol 1986;57:450-458]:

$$LVM = ( (1.04 * ( ( (IVSD + PWD + LVEDD)^3) / 1000 ) - ( (LVEDD^3) / 1000 ) ) - 3.6 ) / ( (WEIGHT^{0.425}) * (HEIGHT^{0.725}) * 0.007184 ) )$$

Where:

IVSD = Interventricular septal thickness at end-diastole (mm)

PWD = Posterior wall thickness at end-diastole (mm)

LVEDD = LV end-diastolic dimension (mm)

Height is expressed in cm and weight in kg.

LVMI will be recalculated from LVM.

Cardiac damage will be assessed according to ESH guidelines [Mancia G, Fagard R, Narkiewicz K, Redón J, Zanchetti A, Böhm M, Christiaens T, Cifkova R, De Backer G, Dominiczak A, Galderisi M, Grobbee DE, Jaarsma T, Kirchhof P, Kjeldsen SE, Laurent S, Manolis AJ, Nilsson PM, Ruilope LM, Schmieder RE, Sirnes PA, Sleight P, Viigimaa M, Waeber B, Zannad F; Task Force Members. 2013 ESH/ESC Guidelines for the management of arterial hypertension: the Task Force for the management of arterial hypertension of the European Society of Hypertension (ESH) and of the European Society of Cardiology (ESC). J Hypertens. 2013 Jul;31(7):1281-357]:

- Males: LVMI > 115 g/m^2
- Females: LVMI > 95 g/m^2

An attempt will also be made to classify left ventricular hypertrophy according to ECG:

- Sokolow-Lyons index: SV1+RV5-6 >38 mm
- Cornell Index; S in V3 + R in aVL >24 mV in males and > 20 mV in females

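### The LVM formula printed in SAP 3.2.1 has one unmatched bracket and can be coded two ways; the literal way raises LVMI by about 2%

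*SAP*

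**What the plan says.** SAP 3.2.1 states: "Cardiac damage will be based on LVMI, calculated as LVM divided by BSA". It then prints one line, labelled LVM. Two opening brackets lead into "1.04 * ( ( (IVSD + PWD + LVEDD)^3) / 1000 ) - ( (LVEDD^3) / 1000 ) ) - 3.6" and one closing bracket follows. This is divided by a weight and height term that ends "HEIGHT^{0.725}) * 0.007184" and two further closing brackets.

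The three echocardiographic dimensions are in millimetres (for the cavity, "LVEDD = LV end-diastolic dimension (mm"). For body size, "Height is expressed in cm and weight in kg". After the formula the SAP adds: "LVMI will be recalculated from LVM". Cardiac damage is then "Males: LVMI > 115 g/m"² or "Females: LVMI > 95 g/m"².

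The data lists in Protocol 4.0, Protocol 14.1 and SAP 2.2 name LVMI as the echocardiographic item. They do not name IVSD, PWD or LVEDD. Neither document gives program code or a worked LVMI value.

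**The concern.** Dimensions in mm, cubed and divided by 1000, are volumes in mL. If 1.04 turns volume into mass, it should apply to the difference between outer and cavity volume. As the brackets stand it applies to the outer volume alone, so millilitres are subtracted from grams.

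The line does not run, so a programmer has to repair it, and the most obvious repair keeps the incoherent form. Two competent programmers could therefore derive different LVMI values from the same SAP.

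The LVMI cut-off is the only echocardiographic criterion for cardiac damage. The relation of blood pressure and arterial stiffness to target organ damage is part of the main analysis (SAP 3) and a project objective (Protocol 7.0). The excess under the literal form grows with the cube of cavity size, so patients with large cavities are shifted most.

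**Working it through.** **Inputs.** Formula, units and cut-offs come from SAP 3.2.1. The documents give no patient dimensions and no LVMI distribution; those used below are assumptions. There is no stated LVMI figure to reproduce.

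**1. Brackets.** The line has 10 opening and 11 closing brackets. The one opened directly after `1.04 *` closes after the first `/ 1000`. The last character of the line has no partner, and typed as printed the line stops with an unmatched-bracket error.

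**2. Two readings.** Let A be the cube of the summed dimensions divided by 1000, B = LVEDD³/1000, and BSA = 0.007184 × weight^0.425 × height^0.725.

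- Literal: (1.04 × A − B − 3.6)/BSA
- Shell volume: (1.04 × (A − B) − 3.6)/BSA
- Literal minus shell: 0.04 × B/BSA, always positive

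**3. Worked example (assumed).** IVSD 10, PWD 10, LVEDD 50 mm; 80 kg; 175 cm.

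- A = 70³/1000 = 343; B = 50³/1000 = 125; BSA = 1.956 m²
- Literal: (356.72 − 125 − 3.6)/1.956 = 228.12/1.956 = 116.6 g/m²
- Shell: (1.04 × 218 − 3.6)/1.956 = 223.12/1.956 = 114.1 g/m²
- Difference: 5.0/1.956 = 2.6 g/m² (2.2%). A man with these values crosses 115.

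**4. What a repair yields.** Deleting each of the 11 closing brackets in turn, on this example:

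| Result (g/m²) | Deletions |
|---|---|
| 116.6 (literal) | 7, including the last bracket |
| 114.1 (shell) | 2 |
| −1.8 or 229.9 (nonsense) | 1 each |

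Inserting an opening bracket after `1.04 *` gives 114.1; inserting it at the far left gives 116.6.

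**5. Range of the shift, 0.04 × B/BSA (g/m²).**

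| LVEDD (mm) | BSA 1.6 | BSA 2.2 |
|---|---|---|
| 40 | 1.6 | 1.2 |
| 50 | 3.1 | 2.3 |
| 60 | 5.4 | 3.9 |

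In eight assumed hearts, with walls of 8 to 12 mm and cavities of 42 to 60 mm, the shift was 2.0 to 2.4% of LVMI.

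**6. Share above the cut-off.** Normal distributions, with shifts of 2.6 g/m² in men and 2.2 g/m² in women, all assumed:

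| Sex | Mean (SD) | Shell | Literal |
|---|---|---|---|
| Men | 95 (22) | 18.2% | 21.4% |
| Men | 105 (25) | 34.5% | 38.4% |
| Women | 85 (20) | 30.9% | 34.8% |
| Women | 90 (22) | 41.0% | 44.9% |

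The rise is 3 to 4 percentage points.

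**7. The recalculation step.** The printed quantity is already divided by BSA. If it is treated as LVM and divided again, the example becomes 116.6/1.956 = 59.6 (literal) or 114.1/1.956 = 58.3 (shell), far below either cut-off.

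**The case against.** A reader might infer that every LVMI in the registry is too high and that hypertrophy is over-diagnosed. The documents do not support that, for four reasons.

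- **The line has no value as printed.** One of the one-character repairs is the coherent formula, and nothing shows that the other was coded.
- **The bracket pattern favours a lost character.** With an opening bracket restored after `1.04 *`, every pair has a role: one closes the volume difference, one the numerator and one the whole expression. On the literal reading, one pair does nothing and the last bracket is an orphan. The text was converted from PDF, and a bracket lost from a run of repeated brackets is a plausible conversion slip.
- **The net direction is not settled.** A second division by BSA would roughly halve LVMI and outweigh a 2% rise.
- **The coverage is unknown.** The data lists collect LVMI and not the three dimensions, so the formula may apply to only some patients.

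The effect is also small. A simulation under assumed dimensions gave a correlation of about 0.9998 between the two forms, so analyses of continuous LVMI would hardly change. No bias in an association with blood pressure or stiffness has been shown.

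All of this stands, and it limits the claim. It does not remove the ambiguity in the line as supplied, which defines a binary outcome. Dropping the orphan bracket is the obvious repair, and it gives the incoherent form.

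**Conclusion.** The formula as supplied is unbalanced and permits two different LVMI values. If the literal form is programmed and BSA is divided out once, LVMI rises by 0.04 × LVEDD³/1000/BSA. That is about 2%, or 1.2 to 5.4 g/m² for assumed cavities of 40 to 60 mm and BSA of 1.6 to 2.2 m². The percentage would be larger where the cavity is large relative to the walls. Only patients within roughly 1 to 5 g/m² of their cut-off would change class: about 3 to 4% under the assumed distributions.

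It is not established that any LVMI is in fact wrong. That depends on the code, on the recalculation step and on the patients to whom the formula is applied. The point should be corrected because the line defines a main organ-damage outcome and the correction is exact. Whether 1.04 and 3.6 match the cited echocardiographic source cannot be checked from the documents, and the conclusion does not rely on it.

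**What to change.** First compare the line with the source file of the SAP, to rule out a PDF-reading slip. Then:

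1. Print, with balanced brackets, LVMI = {1.04 × [(IVSD + PWD + LVEDD)³ − LVEDD³]/1000 − 3.6} / (0.007184 × weight^0.425 × height^0.725).
2. Label the result LVMI, since it is already divided by BSA.
3. Remove or explain the later recalculation of LVMI, so that BSA is not divided out twice.
4. State for which patients the formula is used and where their IVSD, PWD and LVEDD come from. State also what is done when only a reported LVMI is available.
5. Add one worked example as a programming test, such as 10/10/50 mm, 80 kg, 175 cm giving 114.1 g/m², and run the existing code against it.
6. Confirm the constants against the cited source before the example is fixed.

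The formula and the test case cost one SAP line and one example. Items 3 and 4 need a sentence or two each. If the code proves to use another form, LVMI and the cardiac-damage classification must be derived again for the patients concerned.
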